#### B. Feasibility:

The following feasibility data will be collected and assessed :

- 1) Recruitment:
  - a. Recruitment sites (number, location, and method of their selection)
  - b. Factors influencing recruitment rate
  - c. Methods used for subject recruitment
  - d. Number of subjects:
    - i. Initially contacted
    - ii. Initial interviewed

- iii. Consented
- iv. Baseline data collected
- e. Reasons for non-participation:
  - i. After initial contact and/or initial interview
  - ii. After consent process
  - iii. After initial data collection or throughout the study
  - iv. Until end of study
- f. Reasons for participating in and completing study

2) Randomization:

- a. Testing effect of randomization process on distribution of demographic, co-morbidity, and other background characteristics
- c. Testing randomization process on their baseline main outcomes
- d. Examining acceptability of the randomization process and its effect

3) Missing data:

- a. Differences in rates of missing data between medication and placebo groups and per time point
- b. Pattern of missing data

4) Retention rate:

- a. Differences in retention between medication and placebo groups
- b. Factors influencing these differences

5) Subjects' satisfaction with:

- a. Study procedures
- b. Study implementation and staffing
- c. Medication delivery methods
- d. Data collection timepoints and outcomes

6) Medication fidelity with:

- a. Delivery methods
- b. Number of successful and failed deliveries
- c. Assessment methods
- d. Timing and method of feedback

7) Study improvement procedures/maintaining documentation of:

- a. Study/protocol development, revision, and modification
- b. Issues and concerns with implementing recruitment strategies
- c. Issues and concerns with accessing, distributing, and tracking of medication and placebo
- d. Issues and concerns with measurements:
  - i. Number of measurements
  - ii. Time requirements of measurements
  - iii. Redundancy among measurements
  - iv. Positive or negative carryover

Sub-study 1b: mQFPD vs. placebo in acute COVID-19 patients.

The primary objectives of this study are:

- Ascertainment of safety of FoTv and
- Assessment of feasibility of the intervention (with the primary outcomes focusing on determination of the rates of recruitment and completion)

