### **Statistical Methods And Considerations**

For all sub-studies (1a, 1b, and 1c), data management and statistical analysis will be performed by the Krupp Biostatistical and Data Management Core and will employ the Krupp Data System (KDS). A computer-generated randomization list will be prepared by the study biostatistician and will be used to randomize subjects into one of the two treatment groups with equal probability. For sub-study 1c only, equal number of subjects based on age (18-55 and  $>55$ ) and BMI ( $<30$  and  $\geq 30$ ) will be randomized to the treatment groups. For all sub-studies, randomization tables will be prepared at the beginning of the study and will be maintained by the study biostatistician.

Within each of the sub-studies, the comparability of the two treatment groups in terms of baseline demographic and clinical features will be tested with analyses of variance (ANOVAs) for continuous variables and Chi-square analyses for dichotomous variables. Descriptive statistics and exploratory graphing will be used to assess the distribution, normality, and homogeneity of the data. If needed and applicable, the continuous outcome data will be transformed using an appropriate transformation such as a log transformation. Missing data will be examined to assess randomness and informativeness using methods developed by Diggle (1989). Similarly, we will test whether dropout is random or systematic by comparing the dropouts with the study completers in terms of the baseline data. An absence of significant differences would support the random nature of dropout.

The primary aims of our data analytic strategy will be directed toward assessing the safety of the interventions, antibody titers, vaccine side effects, adherence to treatment, and retention rate. This will help to provide guidance to inform any

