A detailed list of feasibility outcomes is provided in the previous section. Briefly, feasibility outcomes will be assessed by determining: 1) Numbers of potentially eligible and ineligible patients, number contacted, and consent rates. 2) Feasibility of recruiting sites in which staff are interested in participating in a future main trial. 3) Rate of retention in the trial, including response rates to questionnaires and individual measures. 4) Intervention fidelity and adherence using case report forms and patient-completed personal diaries. 5) Determining the primary outcome measure for the main trial by assessing and comparing sensitivity to change of the measures and other statistical properties, comparing follow-up rates of different methods of data capture and of individual measures, and evaluating which outcome measures best reflect the patients' recovery goals, as identified from the collected data.

As indicated above, the primary aims of our data analytic strategy for sub-studies 1a and 1b will be directed toward examining the safety and feasibility of the treatments. Although it is not our major focus, we also aim to estimate effect sizes to assist in future power calculations. However, recent work by Kraemer (2006) has highlighted important limitations of this aim due to the large standard error surrounding the pilot study effect size. As a result, the primary focus of our analyses will remain on safety and feasibility and we will report our findings with this limitation in mind. Our goal is to collect important data regarding our ability to implement recruitment strategies, and the safety and feasibility of the treatments and measurements. Information derived from this research will lead to better-designed full-scale studies and help inform decisions regarding whether it is worthwhile to commit additional resources to future treatment development. Due to our small sample size, our statistical analytical findings will be interpreted with caution. Sub-study 1c will include sufficient number of subjects to test for treatment efficacy.

Data will be analyzed from all randomized subjects. All statistical tests will be two-tailed. Differences will be considered statistically significant provided a p-value of 0.05 or less is obtained. The significance level for the tests will be adjusted with a Bonferroni correction for multiple comparisons, if needed. Data will be analyzed using SPSS version 27.

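### Sub-studies 1a and 1b: significance tests on baseline variables are a weak, non-specific check of the randomization process

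*Combined protocol and SAP*

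**What the plan says.** Section 6 (Specific Aims), under B. Feasibility, item 2) Randomization, lists for sub-study 1a, and word for word again for 1b: "Testing effect of randomization process on distribution of demographic, co-morbidity, and other background characteristics". A companion item reads "Testing randomization process on their baseline main outcomes". Neither item names a method.

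The only method for baseline comparisons is in Section 9, Statistical Methods And Considerations. In every sub-study, whether the arms are alike at baseline "will be tested with analyses of variance (ANOVAs) for continuous variables and Chi-square analyses for dichotomous variables". The general rules follow in the same part: "All statistical tests will be two-tailed", and "Differences will be considered statistically significant provided a p-value of 0.05 or less is obtained". A Bonferroni correction is allowed where it is judged necessary, but no family of tests is defined and the baseline tests are not mentioned. The plan does not give the number of baseline variables, an imbalance threshold, or an action to follow a significant result.

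On the standing of the item, feasibility is a primary objective of 1a and 1b, but the aims qualify it: "with the primary outcomes focusing on determination of the rates of recruitment and completion". The short list of feasibility outcomes in the statistical methods leaves randomization out.

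Allocation is by a computer-generated 1:1 list kept by the study biostatistician. Balancing by age and BMI is described for 1c only.

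**The concern.** The feasibility item asks whether the randomization process worked. A baseline significance test asks whether the difference between arms could be chance. If the list was followed, the difference is chance by construction, so a significant result is a false alarm about the process. A non-significant result with 33 per arm does not show that the arms are alike.

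The second misreading is a real risk here. In the same part of Section 9, the lack of significant differences between dropouts and completers is to be taken as support for random dropout. The same inference could easily be carried over to baseline balance.

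At stake is one feasibility finding. Section 9 says the Phase 2 design awaits analysis of 1a and 1b. A sound process could be reported as doubtful, or a moderate imbalance in a prognostic variable could pass without comment because p exceeded 0.05.

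**Working it through.** **Inputs**

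- Sample size: 33 per arm (Section 9). The plan's figure reproduces: 27 × 1.20 = 32.4, rounded up to 33, so 66 in total. Dividing instead, 27 / 0.80 = 33.75, gives 34 per arm and 68 in total, which changes nothing material below.
- Significance level: 0.05, two-sided (Statistical Methods And Considerations).
- Number of baseline tests, k: not stated. As an assumption, the variables listed in Section 9 support about 20: 3 demographic (age, gender, race/ethnicity), 3 comorbidities, 11 laboratory panels or single assays (metabolic panel, liver function, PT, PTT, blood count, ferritin, D-dimer, LDH, CRP, troponin, T-cell panel), plus symptom score, temperature and viral load (3 + 3 + 11 + 3 = 20). The range shown is 5 to 40.

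**Step 1. False flags when the list is followed.** For k independent, unadjusted tests, the chance of at least one is 1 − 0.95^k:

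| k | 5 | 10 | 13 | 14 | 15 | 20 | 30 | 40 |
|---|---|---|---|---|---|---|---|---|
| Chance | 23% | 40% | 49% | 51% | 54% | 64% | 79% | 87% |

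The figure passes one half at k = 14 within a sub-study. Taking 1a and 1b together, 8 variables in each (16 tests) give 1 − 0.95^16 = 56%.

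Correlation lowers these figures. A simulation of equally correlated two-sided z-tests (200,000 draws) gave:

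| Correlation | k = 14 | k = 20 |
|---|---|---|
| 0.3 | 44% | 54% |
| 0.5 | 35% | 42% |

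With Bonferroni over the baseline tests, 1 − (1 − 0.05/k)^k is about 4.9% for k = 14 or 20.

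**Step 2. What goes unflagged at 33 per arm.** The smallest observed difference that reaches significance is t(0.975, 64 df) × √(2/33) = 2.00 × 0.246 = 0.49 SD.

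For a systematic difference of d SD, such as a faulty allocation might create, power by normal approximation is Φ(d/0.246 − z):

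| d | Unadjusted | Bonferroni, k = 14 | Bonferroni, k = 20 |
|---|---|---|---|
| 0.3 SD | 23% | – | – |
| 0.4 SD | 37% | – | – |
| 0.5 SD | 53% | 19% | 16% |
| 0.8 SD | 90% | 63% | 59% |

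For proportions, 20% against 40% has 42% power unadjusted.

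**Step 3. Chance imbalance.** The standard error of a standardized difference is 0.246. The chance that a continuous variable differs by more than 0.25 SD in either direction is 2 × [1 − Φ(0.25/0.246)] = 31%. Only differences beyond 0.49 SD, about 5% of variables, would be flagged. Roughly 31 − 5 = 26% of continuous variables would therefore differ by 0.25 to 0.49 SD without comment.

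**The case against.** The case for leaving the plan alone has four parts.

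- **The false-flag rate is not fixed by the plan.** A reader might infer that a false flag is more likely than not. The documents do not support that. It needs 14 or more roughly independent, unadjusted tests in a sub-study, and no count is given. Several of the laboratory variables are inflammatory or blood-cell measures from one draw, so independence is doubtful. The Bonferroni clause, if it covers these tests, brings the rate to about 5%. This stands, but the clause does not rescue the method: fewer false flags are bought with more missed differences, as Step 2 shows.
- **Little hangs on the item.** A reader might infer that a primary outcome or a Phase 2 decision is compromised. The feasibility outcomes named as primary are recruitment and completion, no rule is tied to the baseline tests, and the plan says results will be read cautiously because the sample is small. This stands and limits the weight of the point.
- **The tests are not empty.** A reader might infer that they carry no information about the process. Every significant result is a false alarm only if the list was followed, which is the matter being checked. A gross failure could produce a large imbalance, and power at 0.8 SD is about 90%. This stands too.
- **Baseline differences in outcomes are partly handled.** The mixed model has individual intercepts and focuses on the treatment-by-time interaction. This stands, so the request on baseline adjustment is secondary.

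None of this makes the tests a sound answer to the question. They cannot tell a chance difference from an allocation error, whereas comparing allocations with the list can.

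**Conclusion.** The point holds as a minor one. The plan judges the randomization process in 1a and 1b by baseline significance tests, and these are a weak and non-specific check. The false-flag chance is 40% to 64% for 10 to 20 independent, unadjusted tests. It is lower with correlation (42% at 20 tests with correlation 0.5) and about 5% with Bonferroni. These figures rest on an assumed number of variables. The 0.49 SD threshold for an observed difference needs no such assumption: it follows from 33 per arm and two-sided 0.05. Small and moderate imbalances will often pass unflagged, and large ones usually will not. No sample size, named primary outcome or decision rule is affected.

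**What to change.** 1. In Statistical Methods And Considerations, replace the baseline ANOVA and chi-square tests with a descriptive table by arm, showing standardized differences and no p-values.
2. In the randomization item of the feasibility lists for 1a and 1b, replace testing on baseline characteristics and baseline outcomes with a check of each allocation, in order and date, against the biostatistician's list. Report the number of allocation errors.
3. State that non-significance will not be taken as evidence of balance.
4. Where a follow-up outcome is compared between arms, account for its baseline value whatever the observed balance. In the mixed model, do not use baseline both as an outcome time point and as a covariate.

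The cost is a change of wording and slightly less analysis. The one addition is that the order and date of each assignment must be recorded, because the documents describe a list but no allocation log.

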#### A. Safety:

The following safety data will be collected and assessed during the study:

- 1) Incidence and severity of adverse events
- 2) Laboratory evaluations
- 3) Home glucometer measurements for diabetic participants
- 4) Home blood pressure measurements for hypertensive participants
- 5) Home daily weight measurements for patients with congestive heart failure or diuretic use

Safety data will be collected and assessed using the following methods:

- 1) Each participant will receive a paper copy and an emailed daily diary requesting information on symptoms (including duration and severity), vitals, and medication compliance. Participants who are unable to respond to emails will be asked to directly record this data into the provided paper study daily diary and then will be contacted daily to report this information to the study coordinator. All email exchanges among study personnel will be conducted within the UC intranet secure system. All communications with patients will be through virtual appointments using UC secure systems, UC San Diego encrypted emails or with password-protected study documents.
- 2) Study coordinators will collect and enter all safety data. All serious adverse events (SAEs) will, per UCSD IRB guidelines, be reported to the IRB and DSMB within 3 business days of learning of the event. Any adverse events, as well as any escalation of care, including urgent care, emergency room, or hospitalization, will be reported to the study team after appropriate medical care has been received, via a dedicated phone number or email address that is specific for urgent matters.
- 3) The UCSD site will implement a Data and Safety Monitoring Board (DSMB) to review data safety and monitoring as part of their responsibilities. The DSMB will include two senior researchers and a consumer representative. They will have conference calls bi-weekly (or more frequently, if needed)
- 4) The study biostatistician will send a tabulated symptom and adverse event report daily to all sites and to the study PI and weekly to the study DSMB and IRB.
- 5) The safety of the study medication will also be assessed through laboratory data collection at baseline, and at either the end of the treatments following end of quarantine (for non-hospitalized patients) or as part of hospital admission labs (for patients requiring hospitalization)
  - e. Basic Metabolic Panel
  - f. Complete Blood Count with Differential
  - g. Liver Function Testing
  - h. Prothrombin Time and Partial Thromboplastin Time

#### B. Feasibility:

The following feasibility data will be collected and assessed :

- 1) Recruitment:
  - a. Recruitment sites (number, location, and method of their selection)
  - b. Factors influencing recruitment rate
  - c. Methods used for subject recruitment
  - d. Number of subjects:
    - I.
      - i. Initially contacted
      - ii. Initial interviewed
      - iii. Consented
      - iv. Baseline data collected
  - e. Reasons for non-participation:
    - i. After initial contact and/or initial interview
    - ii. After consent process
    - iii. After initial data collection or throughout the study
    - iv. Until end of study
  - f. Reasons for participating in and completing study

2) Randomization:

- a. Testing effect of randomization process on distribution of demographic, co-morbidity, and other background characteristics
- f. Testing randomization process on their baseline main outcomes
- g. Examining acceptability of the randomization process and its effect

3) Missing data:

- a. Differences in rates of missing data between medication and placebo groups and per time point
- b. Pattern of missing data

4) Retention rate:

- a. Differences in retention between medication and placebo groups
- b. Factors influencing these differences

5) Subjects' satisfaction with:

- a. Study procedures
- b. Study implementation and staffing
- c. Medication delivery methods
- d. Data collection timepoints and outcomes

6) Medication fidelity with:

- a. Delivery methods
- b. Number of successful and failed deliveries
- c. Assessment methods
- d. Timing and method of feedback

7) Study improvement procedures/maintaining documentation of:

- a. Study/protocol development, revision, and modification
- b. Issues and concerns with implementing recruitment strategies
- c. Issues and concerns with accessing, distributing, and tracking of medication and placebo
- d. Issues and concerns with measurements:
  - i. Number of measurements
  - ii. Time requirements of measurements
  - iii. Redundancy among measurements
  - iv. Positive or negative carryover

Sub-study 1c: FoTv vs placebo for use as an adjunct to COVID-19 vaccination.

The primary objectives of this study are to determine whether FoTv, when taken for four consecutive days starting the day of COVID-19 vaccination, is safe and associated with:

- An enhanced peak COVID-19 antibody response
- A reduced rate of post-peak antibody decline
- Reduction in side effects from COVID-19 vaccination
- Other immunologic (e.g., T-cell mediated) responses

## **7. BACKGROUND AND SIGNIFICANCE**

Despite biomedical advances, medical intervention for COVID-19 is largely limited to supportive care during the later stages of disease. While antiviral, anti-inflammatory, and antimalarial options have been explored for later stages of disease, fewer studies have been conducted on medications to reduce the risk of outpatient cases progressing to severe disease. Therefore, it is important that we broaden the search to include agents outside of our usual pharmacopeia. Integrative Medicine offers several promising therapeutics that are available today and warrant investigation.

Herbal medicines have been used for millennia in China, during which several therapeutic herb combinations have been developed and implemented using Chinese medicine principles. At this time, several of these Chinese Herbal Medicine (CHM) formulas are currently being recommended as part of the Chinese national guidelines to treat COVID-19. CHM

is traditionally prescribed and individualized for treatment following a history and physical examination by a practitioner. In this case, Chinese national guidelines recommend Qing Fei Pai Du Tang (QFPD) as a composite formula consisting of 21 total herbs which can be used broadly for all patients without individualization. As such, QFPD lends itself well to the double blinded RCT trial design. Early clinical trials are promising (Wang, R 2020), however the level of evidence is low. Given the discrepancy between usage and evidence, as well as the need for better therapeutics domestically, high quality trials are warranted. For the purposes of this study, one of the 21 herbs (Kuan Dong Hua) is known to contain potentially toxic pyrrolizidine alkaloids and is of relatively minor therapeutic value, so in an abundance of caution we have substituted a safe alternative, Pi Pa Ye which is known to have a similar clinical effect, to create a modified QFPD or mQFPD.

Some of the botanicals used for their possible immune modulating functions include polypore mushrooms. Among these, Turkey Tail (*Trametes versicolor*) has a long history of use for its immune supporting properties. An RCT examining the effects of *Trametes versicolor* in breast cancer patients detected increases in lymphocyte counts and natural killer cell functional activity (Torkelson et al, 2012 and Benson et al, 2019) both of which are key to host COVID-19 response. Further investigations into other relevant mushroom species demonstrated that Agarikon (*Fomitopsis officinalis*) can strongly induce an array of differential cytokine responses associated with both immune-activation and resolution of host defense- induced inflammatory reactions (unpublished). This homeostatic effect deserves attention for COVID-19 given the high mortality rate associated with cytokine storm.

### *COVID-19 Characteristics*

Coronavirus Disease 2019 (COVID-19) is caused by serious acute respiratory syndrome coronavirus 2 or SARS-CoV-2. A betacoronavirus thought to have been transmitted from rhinophilus bats (Zhou et al., 2020) to humans in Wuhan China, SARS-CoV-2 is a positive-sense single stranded RNA virus. Spike-like surface proteins (coronas) extend from the RNA virus and bind to ACE2 receptors on epithelial cells of the upper respiratory tract and glandular cells in the gastrointestinal tract (Wong, Lui, & Sung, 2020). The effective reproductive number (R0 value) is estimated to be 3.86, (C. Wang et al., 2020) making it highly contagious and has led to a worldwide pandemic that has infected millions of confirmed individuals and caused countless deaths. Transmission can occur through large, virus-laden nuclei in air-borne droplets, physical touch, fomites, (van Doremalen et al., 2020) and possibly, though not confirmed, from fecal sources (Wong et al., 2020). The viral burden peaks early (<2 days) of symptoms based on culture and polymerase chain reaction testing and viral shedding can outlast symptoms and be detected for weeks after symptoms resolve.

Clinical characteristics of COVID-19 include fever, non-productive cough, dyspnea, myalgia, fatigue, nausea, diarrhea, normal or decreased leukocyte counts, and pneumonia confirmed with imaging (N. Chen et al., 2020; Huang et al., 2020; Rodriguez-Morales et al., 2020; C. Wang et al., 2020; D. Wang et al., 2020). In severe cases, patients can experience organ failure and even death in severe cases due to acute respiratory distress syndrome (ARDS) (Huang et al., 2020). Patients aged over 80 and older men are suspected to be at increased risk of experiencing more severe symptoms of COVID-19, especially with comorbidities such as smoking, diabetes, coronary and pulmonary diseases (N. Chen et al., 2020; Rodriguez-Morales et al., 2020). The World Health Organization estimated the unadjusted death rate was 4.0% in China and currently 4.7% worldwide (WHO, 2020).

There is no known cure for COVID-19, but it appears to be a self-limiting disease in 80% of patients (Yuen, Ye, Fung, Chan, & Jin, 2020). In 20% of acute cases requiring hospitalization, conventional treatment in the US is currently symptom management and SARS-CoV-2 viral load reduction in the early phase with the intent of preventing ARDS. COVID-19 prevention and symptom management during early onset of disease are essential to reduce acute care needs and protect hospital resource availability for critically ill cases.

Figure 1 shows the typical time course of COVID-19 patients who ultimately require hospitalization (Zhou et al, 2020). While data on the time course of mild to moderate cases of COVID-19 is more challenging to collect, this figure demonstrates the typical time course of patients that end up with hospitalization and survival (top) or death (bottom). Day 1 on these charts represents the first day that their SARS-CoV-2 RNA test was positive, suggesting several days of positive symptoms prior.

[figure not shown]

Figure 1: Clinical courses of major symptoms and outcomes and duration of viral shedding from illness onset in patients hospitalised with COVID-19

Figure shows median duration of symptoms and onset of complications and outcomes. ICU=intensive care unit. SARS-CoV-2=severe acute respiratory syndrome coronavirus 2. ARDS=acute respiratory distress syndrome. COVID-19=coronavirus disease 2019.

As depicted, there is a 5-7 day window of disease burden during which patients have a confirmed COVID-19 diagnosis but they do not yet require inpatient management. In the US, these patients are assigned to strict home quarantine but no medical options are available aside from symptomatic treatment and supportive care. This represents an optimal population to target experimental therapies which have may modulate immune function and avert or delay the need for hospitalization.

